Title: The effect of lumbar stabilization and walking exercises on chronic low back pain: A randomized controlled trial

NCT number : NCT02938169

Date of document: April, 2017

Materials and Method

This study was a prospective randomized controlled clinical trial with four groups: flexibility exercise (FE) group, walking exercise (WE) group, stabilization exercise (SE) group, and stabilization with walking exercise (SWE) group. Subjects in this study were part of a clinical trial (NCT02938169). The study and all procedures were approved by the Institutional Review Board of Seoul National University Bundang Hospital (B-1604-344- 004).

Subjects This study was conducted between May of 2016 and April of 2017. Patients complaining of chronic LBP were recruited from the rehabilitation outpatient clinic. The inclusion criteria were subjects aged over 20 years with intermittent chronic low back pain of more than 3 months. The exclusion criteria were as follows: a pain intensity of below VAS 40 sease, severe knee or hip arthritis that may interfere with walking exercise, pregnancy, and previous exercise treatment for lumbar paraspinalis muscles within 3 months. The physical examination was done by a PMR specialist.

Sample Size Calculation One way ANOVA power analysis was performed with the help of a statistical team to compare the average values of the four groups. As a result, the power of 82% was obtained when 10 patients were allocated to each group. As a result, 15 patients were assigned to each group to account for a dropout rate of 30%.

Randomization Consenting participants were randomly allocated to one of four study groups, following the predetermined and computer-generated random allocation sequences that were prepared by a statistician not involved in participant recruitment. The randomization schedule was only accessible by two individuals: the statistician and the primary investigators.

Blinding It was not possible to blind participants and physiotherapists given the nature of the exercise therapy and evaluation. One researcher blinded to group allocation measured the outcomes at pre-, immediately post-, and 6 weeks post-exercise program. Statisticians and primary investigators were unaware of the group allocation until data analyses were complete.

Exercise protocol Participants underwent each exercise for 30~60 minutes, 5 times a week, for a

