total duration of 6 weeks. All participants were educated on the correct posture and abdominal bracing method, and received a pamphlet explaining good postures and abdominal bracing method for preventing LBP. Light abdominal bracing exercise (10-20% of maximal bracing) was recommended for all times; maximal bracing was recommended for 5-7 seconds, intermittently. The education session was performed at the clinic by a trained physical therapist at the first visit. Moreover, a printed pamphlet with instructions on how to perform the exercises was given to each patient. The exercises were performed at home. All participants underwent a telephone interview every two weeks to confirm the current pain status, degree of exercise compliance, and to adjust the exercise level. Telephone communication also acted as an encouragement to exercise, promoting compliance.

The FE group received stretching exercise for the abdominal muscle, quadriceps, hamstring, tensor fascia lata, piriformis muscle, and quadratus lumborum muscles for 30 minutes. The WE group performed fast walking on flat ground with abdominal bracing for 30 minutes. The SE group was educated on IGLSE, focusing on the modifiable intensity level based on the exercise capacities of each participant. The IGLSE protocol consisted of two parts: stretching exercises and stabilization exercises. All participants performed stretching exercises for 5 minutes as a warm-up before beginning the stabilization exercises for 25 minutes. This program ranged from easy to difficult, based on participants' exercise capacity. Each exercise level had seven basic positions: supine, dead bug, side lying, prone, bird dog, bridge, and plank (five levels). We gradually increased the degree of instability until the most unstable posture was achieved. At the beginning, participants were placed into a level with moderate difficulty. To challenge the stabilization of all trunk muscles (anterior, lateral, and posterior), including the transverse abdominis, rectus abdominis, erector spinae and multifidus, internal oblique abdominals, and quadrates lumborum, participants were instructed to complete all five exercise positions in each session. Patients repeated each of the 7 postures 5 times for about 30 seconds each, to the best of their ability, for a total of 25 minutes.^{12, 13} The SWE group performed IGES for 30 minutes and walking for an additional 30 minutes.

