Outcome measurement The primary outcome was the changes of VAS of LBP from the baseline to the follow-up. VAS was measured during rest and physical activity. The secondary outcomes included VAS of radiating pain measured during rest and physical activity, frequency of medication use (number of taking medications / day), endurance of specific posture (squared posture), and strength of lumbar extensor muscles. Endurance was measured in three postures (supine, side-lying, and prone)¹². The strength of lumbar extensor was measured with the manual muscle

tester (FEI 12-0380 Lafayette® Manual Muscle Tester, Fabrication Enterprises Inc., USA) in sitting position. In addition, Oswestry disability index and Beck depression inventory were measured to identify kinesiophobia, psycho-social aspects, and the disability for low back pain.

The first follow-up evaluation was done within 2 weeks after the completion of the 6-week exercise program, and all the initial evaluations were rechecked (immediately post-exercise program). The second follow-up evaluation was performed 12 weeks after the start of the program (6 weeks post-exercise program). At this evaluation, frequency and duration of exercise, as well as VAS of back pain and radiating pain during rest and physical activity were rechecked via telephone questionnaire to investigate the long-term compliance and effectiveness of the exercise treatment. Participants were advised to continue the exercise routine for the full duration of the program and that the second follow-up evaluation would be performed at the 12-week.

Statistical Methods SPSS 21.0 software (SPSS Inc, Chicago, IL, USA) was used for all statistical analyses. Wilcoxon signed rank test was used to compare the variables before and after the exercise in each group. Kruskal-Wallis test was used to compare the four groups. Repeated measures ANOVA was used to compare the pain scores (VAS) at various time points: first week (pre-exercise program), sixth week (immediately post-exercise program), and twelfth week (6 weeks post-exercise program). The results are presented as the mean \pm standard deviation. P values of less than 0.05 were considered statistically significant.

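### The plan expects 30% dropout but names no analysis population or missing-data method, and its repeated measures ANOVA would by default discard pain scores already collected

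*Combined protocol and SAP*

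**What the plan says.** Sample Size Calculation reports that "the power of 82% was obtained when 10 patients were allocated to each group" and that "15 patients were assigned to each group to account for a dropout rate of 30" per cent. Dropout is not defined, and nothing says whether a participant who stops the home exercises counts as one.

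Outcome measurement defines the endpoint: "The primary outcome was the changes of VAS of LBP from the baseline to the follow-up". VAS is taken at rest and during activity, at baseline, after the six-week programme, and by telephone at week 12.

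Statistical Methods names three procedures in SPSS 21.0. For within-group change, "Wilcoxon signed rank test was used to compare the variables before and after the exercise in each group". Kruskal-Wallis compares the four groups. For the time course, "Repeated measures ANOVA was used to compare the pain scores (VAS) at various time points", namely the first, sixth and twelfth weeks. The section gives no analysis population, missing-data method, imputation or sensitivity analysis, and does not name the SPSS procedure behind the ANOVA.

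On contact during the programme, Exercise protocol says: "All participants underwent a telephone interview every two weeks to confirm the current pain status, degree of exercise compliance".

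**The concern.** Enrolling extra participants to cover dropout protects power. It does not protect the randomised comparison if those lost differ from those kept. Here the outcome is self-reported, participants know their treatment, and the exercise is done at home. Sessions last 30 minutes in three arms and 60 minutes (30 plus 30) in the combined stabilization and walking arm, so unequal loss between arms is plausible, though not documented.

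The repeated measures ANOVA is the only named analysis that uses all three time points, and it is the one most exposed. In its classical form, a participant with baseline and week-6 scores who cannot be reached at week 12 is removed entirely. If people in more pain at week 6 are harder to reach later, the week-6 mean in that analysis describes a group in less pain than the one actually measured. If this happens in some arms and not others, it enters the group-by-time comparison.

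**Working it through.** **The plan's own figure.** Inputs: 10 evaluable per group and 30% dropout (Sample Size Calculation). 10 / (1 − 0.30) = 14.29, rounded up to 15 per group, 60 in all. This reproduces. At exactly 30% dropout, 15 × 0.70 = 10.5 per group remain, 42 of 60, and 18 are incomplete.

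**Power is not the issue.** No effect size or SD is given, so the 82% cannot be checked. Solving the one-way ANOVA (4 groups, 10 each, alpha 0.05) for 82% gives f = 0.564. With that back-solved value, power at 10.5 per group is 84%.

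**Observed scores discarded, per VAS item.** The 42 complete participants supply 42 × 3 = 126 scores.

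| When the 18 are lost | Observed | Discarded | Share | Week-6 scores discarded |
|---|---|---|---|---|
| All before week 6 | 126 + 18 = 144 | 18 | 12.5% | 0 |
| Half before, half after | 126 + 9 + 18 = 153 | 27 | 17.6% | 9 |
| All after week 6 | 126 + 36 = 162 | 36 | 22.2% | 18 |

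**Bias if loss depends on pain.** None of these inputs is in the documents; all are assumed. True means are 60, 40 and 40 mm at baseline, week 6 and week 12; SD is 20 mm; 30% are lost after week 6, with log-odds of loss rising by 1 per SD of week-6 VAS. In simulation the completers' week-6 mean is 34.95 mm, which is 5.05 mm below the true 40. Because the other visits are correlated with week 6, their completer means shift by the correlation times 5.05. Write r(0,6) and r(6,12) for the correlations of week 6 with baseline and with week 12.

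- Week-6 change is overstated by 5.05 × (1 − r(0,6)). At 0.5 this is 2.5 mm; at 0.7 it is 1.5 mm. Simulated completer improvements are 22.5 and 21.5 mm against a true 20.
- Week-12 change is overstated by 5.05 × (r(6,12) − r(0,6)). With equal correlations this is 0 (simulated 20.0). With r(0,6) = 0.6, r(6,12) = 0.7 and a baseline to week-12 correlation of 0.4, it is 0.5 mm (simulated 20.5).
- Week-6 change in everyone observed at week 6, which is what Wilcoxon or Kruskal-Wallis on that change would use, is 20.0 mm.
- With loss unrelated to pain, completer changes at both visits are 20.0 mm.
- Predicting week 12 from baseline and week 6, which is how a mixed model uses the partial records, returns 20.0 mm in each setting.

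**Between arms.** If pain-related loss is the same in every arm, the shift largely cancels between groups. If it occurs in only one of two arms, a spurious week-6 difference of 1.5 to 2.5 mm appears. For scale, the SD of change is 20 × √(2 × (1 − correlation)), or 20.0 and 15.5 mm. At 15 per arm the standard error of a difference is that SD × √(2/15), or 7.3 and 5.7 mm. The bias is therefore about 0.35 and 0.27 of a standard error.

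**The case against.** Several stronger readings are tempting, and the documents do not support them.

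- A reader might infer that people who stop exercising are not followed up. The two-weekly calls go to all participants and ask about pain and compliance, and the week-12 call records exercise frequency and duration together with VAS. Neither is limited to those still exercising. What is missing is an explicit rule.
- A reader might infer that someone who misses the first follow-up has no later score. Nothing makes the week-12 telephone VAS depend on attending at week 6.
- A reader might infer that every named test discards data in the same way. Wilcoxon and Kruskal-Wallis on week-6 change need only baseline and week 6, so they keep those scores when week 12 is missing. At a given time point they use the same participants as each other, so the contrast is between them and the ANOVA.

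Three further points have force. Deletion of incomplete cases is the default of the classical routine, but the plan names no procedure and does not rule out another approach. The 30% is a planning allowance, not an observed loss. The simulated bias is small beside sampling error and is mainly at week 6.

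The core stands all the same: heavy loss is expected, no analysis population or missing-data method is stated, and the named analysis by default discards observed scores. A mixed model is not more demanding in its assumptions, since repeated measures ANOVA already relies on approximate normality.

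**Conclusion.** The point holds in a limited form. The omission of an analysis population and a missing-data method is a fact of the text. The discarding of observed scores follows from the SPSS default and amounts to 12.5% to 22.2% of observed scores per VAS item at 30% dropout, depending on when the loss occurs.

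Bias is conditional. Under the assumed SD, correlations and pain-related loss, the ANOVA's week-6 improvement is too favourable by about 1.5 to 2.5 mm, and the week-12 change by 0 to about 0.5 mm. It would be wrong to conclude that the primary comparison is invalid, or that the results describe only those who kept exercising.

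These figures assume that loss depends on pain already recorded at week 6. If it depends on pain never recorded, bias could be larger and no analysis of the observed data would remove it. The change is worth making because it is cheap and uses data already collected.

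**What to change.** In Statistical Methods, replace the repeated measures ANOVA with a linear mixed model for repeated measures (SPSS MIXED) with group, time and group-by-time, fitted to rest and activity VAS separately. State that it uses every observed VAS from all randomised participants in their allocated group, regardless of exercise adherence.

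Report missing VAS by arm, time point and reason. Add a sensitivity analysis over a range of assumed outcomes for missing values. For example, if those missing are 10, 20 or 30 mm worse than completers, a completer arm mean at 30% missing is too favourable by 0.30 × 10, 20 or 30 = 3, 6 or 9 mm. Setting missing change to zero should not stand alone: in the scenario above with equal correlations it turns a true 20 mm week-12 improvement into 0.70 × 20 = 14 mm.

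The document is dated April 2017, the month in which it says the study ended, and is written in the past tense, so new data collection may no longer be possible. If follow-up is still open, state that stopping exercise is not withdrawal from the study, and that week-6 and week-12 VAS are still sought through the existing calls.

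The cost is revised wording, one alternative procedure in the same software and one extra table. The downside is slightly more analysis work and possibly less favourable estimates. The sample size does not change.
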